#### **Description:**

- The purpose of this RAP is to describe the planned analyses and output to be included in the Clinical Study Report for Protocol 201312
- This RAP will be provided to the study team members to convey the content of the Statistical Analysis Complete (SAC) deliverable.

### 1. INTRODUCTION

The purpose of this reporting and analysis plan (RAP) is to describe the analyses to be included in the Clinical Study Report for Protocol 201312.

Revision Chronology:				
GSK Document Number	DD-MMM-YYYY	Version		
2013N187987_00	11-FEB-2014	Original		
2013N187987_01	27-JUN-2014	Amendment No. 1		
2013N187987_02	14-NOV-2014	Amendment No. 2		
2013N187987_03	19-JUN-2015	Amendment No. 3		
2013N187987_04	06-JUL-2015	Republishing Protocol Amendment 3		

### 2. SUMMARY OF KEY PROTOCOL INFORMATION

### 2.1. Changes to the Protocol Defined Statistical Analysis Plan

There were no changes or deviations to the originally planned statistical analysis specified in the protocol amendment 3 (Dated: 06/JUL/2015).

### 2.2. Study Objective(s) and Endpoint(s)

Objectives	Endpoints
Primary Objectives	Primary Endpoints
To provide extended treatment with mepolizumab to subjects with a history of life-threatening or seriously debilitating asthma and a history of improved disease control while receiving mepolizumab as defined in the protocol.	
 
Annualized rate of exacerbations
 
Frequency of adverse events
 

Secondary Objectives	Secondary Endpoints
To further describe the long- term clinical experience of mepolizumab in a subset of subjects who demonstrated significant clinical benefit since receiving mepolizumab	
 
Asthma Control Questionnaire-5 score
 
Forced expiratory volume in 1 second (FEV1)
 
Number of withdrawals due to lack of efficacy
 
Number of withdrawals due to adverse events
 
Number of hospitalizations due to adverse events including asthma exacerbations
 
Frequency of both systemic (i.e., allergic and non-allergic) and local site reactions
 
12-lead ECG parameters
 
Vital signs
 
Frequency of positive anti-mepolizumab binding antibodies/neutralizing antibodies
 

Objectives	Endpoints	
	Clinical Laboratory Parameters	

### 2.3. Study Design

Overview of Study Design and Key Features				
Design	Study 201312 is a study of subcutaneously (SC) administered			
Features	mepolizumab 100mg that will enrol a subset of subjects from Study			
	MEA115661 who have demonstrated clear benefit from therapy and who			
	without continuation of mepolizumab therapy are individuals at greatest			
	risk of serious deterioration of their health status.			
	This is a multi-centre, open-label, long-term study of mepolizumab 100mg			
	administered SC, in addition to standard of care (SOC), in subjects with			
	severe eosinophilic asthma. Only subjects who complete the MEA115661			
	Exit Visit (Visit 14) and meeting all eligibility criteria will be offered the			
	opportunity to consent for this study of up to 172 weeks.			
Dosing	Mepolizumab 100 mg SC will be administered approximately every 4			
_	weeks with the first dose administered at Week 0 (Visit 1) and the last dose			
	administered at Week 168 (Visit 43).			
	Forty-three doses will provide therapeutic coverage for 172 weeks (4			
	weeks following the last dose).			
	Subjects will continue to receive mepolizumab 100mg SC injections for up			
	to 172 weeks or until one of the following occurs:			
	• the risk/benefit profile for the subject is no longer positive in the			
	opinion of the investigator or			
	• the subject's physician withdraws the subject or			
	• the subject withdraws consent or			
	• the sponsor discontinues development of mepolizumab or			
	• the sponsor discontinues the study in the relevant participating			
	country or			
	• mepolizumab becomes commercially available in the local country.			
	The study closure process will begin, on a country by country basis, as			
	mepolizumab becomes commercially available for prescription.			
Time &	Refer to Appendix 1: Schedule of Activities			
Events				
Treatment	All subjects are assigned to 100 mg SC mepolizumab.			
Assignment				
Interim	No interim analysis was conducted.			
Analysis				

### 2.4. Statistical Hypotheses

Since the study has a single treatment arm, statistical analyses of treatment effect will not be performed. Therefore, no hypotheses have been defined for this study.

### 3. PLANNED ANALYSES

### 3.1. Interim Analyses

While the protocol allowed for interim analyses to be performed as needed in order to provide open-label safety data to inform the risk-benefit assessment of mepolizumab in severe asthma, no interim analysis was required or conducted.

### 3.2. Final Analyses

The final planned primary analyses will be performed after the completion of the following sequential steps:

1. All subjects have been withdrawn from the study as defined in the protocol.

2. All required database cleaning activities have been completed and final database. release and database freeze has been declared by Data Management.

### 4. ANALYSIS POPULATIONS

Population	Definition / Criteria	Analyses Evaluated
All Subjects Enrolled (ASE)	The population will comprise all subjects for whom a record exists on the database.	Screen failures
As Treated (AT)	The population will consist of all subjects who received at least one dose of an open label mepolizumab within study 201312.	
 
Study Population
 
Efficacy
 
Pharmacodynamic
 
Safety
 

Refer to Appendix 10: List of Data Displays which details the population used for each display.

### 4.1. Protocol Deviations

Protocol deviations will be tracked by the study team throughout the conduct of the study in accordance with the Protocol Deviation Management Plan [Version 4 (24/AUG/2017)].

- Data will be reviewed prior to freezing the database to ensure all important deviations and deviations are captured and categorised on the protocol deviations dataset.
- This dataset will be the basis for the summaries and listings of protocol deviations.

Important protocol deviations (including deviations related to study inclusion/exclusion criteria, conduct of the trial, patient management or patient assessment) will be summarised and listed.

A separate summary and listing of all inclusion/exclusion criteria deviations will also be provided. This summary will be based on data as recorded on the inclusion/exclusion page of the eCRF.

### 5. CONSIDERATIONS FOR DATA ANALYSES AND DATA HANDLING CONVENTIONS

### 5.1. Study Treatment & Sub-group Display Descriptors

Treatment Group Descriptions								
	RandAll NG	Data Displays for Reporting						
Code	Description	Description	Order 					
1	Mepolizumab 100mg SC	Mepolizumab 100mg SC	1					

NOTES:

1. Order represents treatments being presented in TFL, as appropriate.

### 5.2. Visit 1 Assessments (Copying from MEA115661)

Subjects will enter this study (201312) after completion of the MEA115661 study. To reduce the burden of repeated procedures during the ending of MEA115661 and the start of 201312, some baseline assessments will be copied from MEA115661. Detailed conditions for copying assessments are listed below:

#### Definition 1.

**Condition:** 

i) Visit 1 Date is less than/equal to 8 weeks apart from the MEA115661 Visit 14 (Exit Visit) Date;

ii) MEA115661 Visit 15 (Follow Up) Visit assessment is not available;

Action: Copy assessment from MEA115661 Visit 14 (Exit Visit)

Definition 2.

### **Condition:**

i) Visit 1 Date is less than/equal to 8 weeks apart from the MEA115661 Visit 14 (Exit Visit) Date;

ii) MEA115661 Visit 15 (Follow Up) Visit assessment is available;

Action: Copy assessment from MEA115661 Visit 15 (Follow Up) Visit

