6.1. Critical Baseline Assessments

Baseline assessments performed for scenario 1 subjects in study 201312:

1. Demographic information review and update for 201312

2. General medical history review and update in 201312
3. Physical examination and update in 201312
4. Assessment of Inclusion/Exclusion criteria.
5. Urine pregnancy test for females of childbearing potential ([Appendix 2: Acceptable Birth Control](#))

Baseline assessments performed for scenario 2a subjects in study 201312:

1. Demographic information review and update for 201312
2. General medical history review and update in 201312
3. Physical examination and update in 201312
4. Pulmonary function tests and assessment
5. Assessment of Inclusion/Exclusion criteria.
6. Urine pregnancy test for females of childbearing potential ([Appendix 2: Acceptable Birth Control](#))

For scenario 2b subjects in study 201312, the following assessments should be performed:

1. Demographic information review and update for 201312
2. General medical history review and update in 201312
3. Physical examination and update in 201312
4. Pulmonary function tests and assessment
5. Assessment of Inclusion/Exclusion criteria.
6. Asthma Control Questionnaire-5 (Section [6.2.1.2](#))
7. Vital signs (Section [6.3.10.3](#))
8. 12-lead ECG (Section [6.3.10.4](#))
9. Blood sampling for the following:
 - Clinical chemistry
 - Hematology
 - Liver Analytes
 - Immunogenicity
10. Urine pregnancy test for females of childbearing potential ([Appendix 2: Acceptable Birth Control](#))

Please see the SPM for more detail around the required baseline assessments.

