### Definition 3.

Condition:

i) Visit 1 Date is greater than 8 weeks apart from the MEA115661 Visit 14 (Exit Visit) Date;

ii) MEA115661 Visit 15 (Follow Up) Visit Date is equal to the Visit 1 Date; **Action:** Copy assessment from MEA115661 Visit 15 (Follow Up) Visit

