### Definition 4.

#### Condition:

i) Visit 1 Date is greater than 8 weeks apart from the MEA115661 Visit 14 (Exit Visit) Date;

ii) Visit 1 Date is after the MEA115661 Visit 15 (Follow Up) Visit Date Action: New assessments to be performed at Visit 1, no copying from MEA115661 will be performed

Under definitions 1-3, a number of the following baseline assessments will be copied from either MEA115661 Visit 14 (Exit Visit) or MEA115661 Visit 15 (Follow Up Visit) where available:

- Pulmonary function test data (including FEV1 and FVC)
- Asthma Control Questionnaire-5 (ACQ-5)
- Vital Sign data
- ECG data
- Laboratory data (including Haematology, Chemistry and Liver Event test panels)
- Immunogenicity data

The remaining baseline assessments will need to be performed at Visit 1 of the 201312 study, in which case, no copying from MEA115661 study will be performed. A list of the remaining baseline assessments based on each definition can be found in Appendix 5: Derived and Transformed Data.

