### 5.3. Baseline Definition

Baseline will be defined for all subjects who are within the AT population.

The baseline assessment for each subject will be derived as the latest assessment prior to first dose of mepolizumab in this study. If the measurements are taken on the same date as the first administration of mepolizumab, they will be considered within the baseline derivation if measurement time is not captured. Where the measurement time is captured this should be compared against the time of first receiving mepolizumab.

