### 5.3.1. Derivations and Handling of Missing Baseline Data

Definition	Reporting Details
Change from Baseline	= Visit Value – Baseline Value
Ratio to Baseline	= Visit Value / Baseline Value

NOTES :

 Unless otherwise specified, the baseline definitions specified in Section 5.3 (Baseline Definition) will be used for endpoints / parameters and indicated on summaries and listings.

• Unless otherwise stated, if baseline data is missing no derivation will be performed and will be set to missing.

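### SAP 5.2 Definition 2 copies the MEA115661 Visit 15 value whenever one exists, with no check that it precedes the first 201312 dose and no fallback to Visit 14, so a baseline can be lost although a valid Visit 14 value exists

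*SAP*

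**What the plan says.** SAP 5.2 sorts subjects into four definitions and names the source of the Visit 1 values for each.

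- Definition 2 applies when "Visit 1 Date is less than/equal to 8 weeks apart from the MEA115661 Visit 14 (Exit Visit) Date" and "MEA115661 Visit 15 (Follow Up) Visit assessment is available". The instruction is "Action: Copy assessment from MEA115661 Visit 15 (Follow Up) Visit".
- Definition 3 (entry after 8 weeks) also copies Visit 15, but only if "MEA115661 Visit 15 (Follow Up) Visit Date is equal to the Visit 1 Date".
- Definition 4 (entry after 8 weeks) copies nothing, and applies if "Visit 1 Date is after the MEA115661 Visit 15 (Follow Up) Visit Date".

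The copied data types are lung function, ACQ-5, vital signs, ECG, laboratory data and immunogenicity.

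SAP 5.3 then says that baseline is "derived as the latest assessment prior to first dose of mepolizumab in this study". A same-day value counts if no measurement time was recorded; otherwise its time is compared with the dosing time. Under 5.3.1, "if baseline data is missing no derivation will be performed and will be set to missing".

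Protocol 3.1 places the first dose at Visit 1 and lets scenario 1 subjects have Visit 1 on the same day as Visit 14 or up to 8 weeks later. Inclusion criterion 4 (Protocol 4.2) requires completion of Visit 14 and does not mention Visit 15.

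**The concern.** Of the three definitions that involve an existing Visit 15, Definition 2 alone does not tie its date to Visit 1. It asks only whether the assessment exists. Because dosing starts at Visit 1, a Visit 15 held after Visit 1 is a post-dose measurement in 201312, yet Definition 2 would still file it as the Visit 1 value. Section 5.3 then refuses it as baseline. The Visit 14 value, which would have qualified, has not been copied, and neither section says to go back for it.

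The outputs at risk are those that need a baseline:

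- baseline lung function (Table 1.11);
- change in ACQ-5 and FEV1 (Tables 3.10 and 3.11);
- the eosinophil ratio to baseline (Table 4.1);
- laboratory, ECG and vital-sign changes;
- the treatment-emergent antibody summary (Table 2.66), which depends on results before the first dose.

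Two programmers working from the same text could handle an affected subject differently.

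**Working it through.** No sample-size or power arithmetic applies. The check traces the rules over the possible orders of the visits.

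**Inputs.** Days are counted from Visit 14 (day 0). Visit 1 is the day of first dose (Protocol 3.1). Definition 2 requires Visit 1 on or before day 8 × 7 = 56. The MEA115661 schedule for Visit 15 is not in the documents, so the Visit 15 days below are illustrative.

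**Two readings of 5.3.** Reading A applies 5.3 only to the value that 5.2 has copied. Reading B lets 5.3 search all MEA115661 records, including Visit 14. The SAP does not say which is meant.

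| Visit 1 day | Visit 15 day | Copied Visit 15 value is | Baseline, reading A | Baseline, reading B | Baseline with the date check |
|---|---|---|---|---|---|
| 42 | 35 | pre-dose | Visit 15 | Visit 15 | Visit 15 |
| 56 | 49 | pre-dose | Visit 15 | Visit 15 | Visit 15 |
| 56 | 56 | same day | Visit 15* | Visit 15* | Visit 15* |
| 28 | 56 | post-dose | missing | Visit 14 | Visit 14 |
| 0 | 56 | post-dose | missing | Visit 14* | Visit 14* |
| 56 | 63 | post-dose | missing | Visit 14 | Visit 14 |

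*Subject to the same-day time rule in 5.3.

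**What follows.**

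1. When Visit 15 precedes Visit 1, Definition 2 selects the latest pre-dose value and agrees with 5.3.
2. When Visit 15 follows Visit 1, Definition 2 supplies a value that 5.3 rejects. Under reading A the baseline is missing and 5.3.1 sets the derived changes to missing. Under reading B nothing is lost.
3. In every case where a baseline is lost, a Visit 14 value exists that is at most 56 days old at first dose.
4. The conflict does not depend on the Visit 15 days chosen. If Visit 1 is on the same day as Visit 14, which scenario 1 allows, any Visit 15 held on a later day is post-dose.

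**The case against.** The best defence is the opening of SAP 5.2, which says that entry to 201312 follows completion of MEA115661. On that premise an available Visit 15 precedes Visit 1, and Definition 2 is right. But the protocol uses completion to mean completion through Visit 14 (Protocol 3.2, and inclusion criterion 4), so the premise does not guarantee the order.

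The second defence is that 5.3 already bars a later-dated value, and that the SAP draws on earlier-study data elsewhere (for example in 7.1 and 8.1.5.1). The first half stands. A reader might infer that a post-dose value would serve as baseline, but 5.3 does not allow that. What remains is a missing baseline, and only if 5.3 is not read as reaching back to Visit 14.

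Three further inferences are tempting, and the documents do not support them.

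- *Visit 15 always falls more than 8 weeks after Visit 14, so every Definition 2 copy is post-dose.* Scenario 2a and Definition 3 show that timing only because they select subjects with Visit 1 after 8 weeks and Visit 15 on the same day. They say nothing about Definition 2 subjects. Nor does the current protocol tell a subject already dosed in 201312 to return for Visit 15.
- *Definition 2 subjects lose baseline FEV1.* The list in Protocol 6.1 headed "Baseline assessments performed for scenario 2a subjects in study 201312" repeats lung function but not the other copied data types, which might suggest that Visit 15 had no spirometry. But Definitions 1 and 2 turn on whether the Visit 15 assessment is available, and 5.2 copies items where available. If Visit 15 had no spirometry, that assessment falls under Definition 1 and Visit 14 is copied. In addition, SAP 11.5.1 has a list between those for Definitions 1 and 4 that includes lung function tests at Visit 1. Its heading is not legible in the text reviewed, and it may cover Definition 2.
- *A subject entering after 8 weeks with no Visit 15 on or before Visit 1 fits no definition.* That is true of the wording, but scenarios 2a and 2b both presuppose a Visit 15, so the case is hypothetical here.

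**Conclusion.** The gap is real and limited. Definition 2 can conflict with 5.3 in a visit sequence that the protocol permits, and the SAP does not say how to resolve it. A baseline is lost only if two things hold together: Visit 15 took place after the first 201312 dose, and 5.3 is applied only to the copied value.

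The number of affected subjects cannot be derived from the documents and may be zero; any percentage would be a guess. For an affected subject, the loss covers the copied data types that were collected at Visit 15.

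The two primary endpoints, the annualised exacerbation rate and adverse event frequency, do not use this baseline. By-visit absolute ACQ-5 and FEV1 values are also unaffected after Visit 1. The study is single-arm and descriptive with no hypotheses (SAP 2.4), so no test result depends on the point. It should still be corrected, because a usable pre-dose value could go unused and the remedy needs no new data.

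**What to change.** Reword Definition 2 so that it applies separately to each assessment type: copy the Visit 15 value only if it is dated before the first 201312 dose, with same-day values handled as in 5.3; in all other cases copy the Visit 14 value. A count of subjects by baseline source (Visit 14, Visit 15 or new at Visit 1) in the study report would show whether the situation occurred.

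The cost is one or two lines in SAP 5.2 and a date comparison in the copy program, using dates and values already held.

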### Definition 3.

Condition:

i) Visit 1 Date is greater than 8 weeks apart from the MEA115661 Visit 14 (Exit Visit) Date;

ii) MEA115661 Visit 15 (Follow Up) Visit Date is equal to the Visit 1 Date; **Action:** Copy assessment from MEA115661 Visit 15 (Follow Up) Visit

### Definition 4.

#### Condition:

i) Visit 1 Date is greater than 8 weeks apart from the MEA115661 Visit 14 (Exit Visit) Date;

ii) Visit 1 Date is after the MEA115661 Visit 15 (Follow Up) Visit Date Action: New assessments to be performed at Visit 1, no copying from MEA115661 will be performed

Under definitions 1-3, a number of the following baseline assessments will be copied from either MEA115661 Visit 14 (Exit Visit) or MEA115661 Visit 15 (Follow Up Visit) where available:

- Pulmonary function test data (including FEV1 and FVC)
- Asthma Control Questionnaire-5 (ACQ-5)
- Vital Sign data
- ECG data
- Laboratory data (including Haematology, Chemistry and Liver Event test panels)
- Immunogenicity data

The remaining baseline assessments will need to be performed at Visit 1 of the 201312 study, in which case, no copying from MEA115661 study will be performed. A list of the remaining baseline assessments based on each definition can be found in Appendix 5: Derived and Transformed Data.

### 5.3. Baseline Definition

Baseline will be defined for all subjects who are within the AT population.

The baseline assessment for each subject will be derived as the latest assessment prior to first dose of mepolizumab in this study. If the measurements are taken on the same date as the first administration of mepolizumab, they will be considered within the baseline derivation if measurement time is not captured. Where the measurement time is captured this should be compared against the time of first receiving mepolizumab.

### 5.3.1. Derivations and Handling of Missing Baseline Data

Definition	Reporting Details
Change from Baseline	= Visit Value – Baseline Value
Ratio to Baseline	= Visit Value / Baseline Value

NOTES :

 Unless otherwise specified, the baseline definitions specified in Section 5.3 (Baseline Definition) will be used for endpoints / parameters and indicated on summaries and listings.

• Unless otherwise stated, if baseline data is missing no derivation will be performed and will be set to missing.

### 5.4. Multicentre Studies

The following regions are defined with consideration for standard of care medical practice, number of subjects enrolled and regulatory considerations:

Region	Countries
European Union	Belgium, Czech-Republic, France, Germany, Italy, Netherlands, Poland, Spain, Ukraine, United Kingdom
Rest of World	Argentina, Australia, Canada, Chile, Japan, Russia, South Korea, United States

### 5.5. Examination of Subgroups

The list of subgroups may be used in descriptive summaries and safety analyses. Additional subgroups of clinical interest may also be considered.

Subgroup	Categories
Age group	12-17,18-64, >=65 years

# 5.6. Other Considerations for Data Analyses and Data Handling Conventions

Other considerations for data analyses and data handling conventions are outlined in the appendices:

Section	Component
11.1	Appendix 1: Schedule of Activities
11.2	Appendix 2: Assessment Windows
11.3	Appendix 3: Treatment Phases
11.4	Appendix 4: Data Display Standards & Handling Conventions
11.5	Appendix 5: Derived and Transformed Data
11.6	Appendix 6: Reporting Standards for Missing Data
11.7	Appendix 7: Values of Potential Clinical Importance
11.8	Appendix 8: Model Checking and Diagnostics for Statistical Analyses

### 6. STUDY POPULATION ANALYSES

### 6.1. Overview of Planned Study Population Analyses

The study population analyses will be based on the As Treated (AT) population, unless otherwise specified.

Study population analyses including analyses of subject's disposition, demographic and baseline characteristics, medical history, concomitant medications and protocol deviations will be based on GSK Core Data Standards. Details of the planned displays are presented Appendix 10: List of Data Displays.

### 6.2. Subject Disposition

A summary of the number of subjects included in each population will be produced.

The proportion of screen failures, the proportion who reported each reason for screen failure and the proportion who failed each eligibility criteria will be presented for the All Subject Enrolled (ASE) population.

The proportion of subjects in the AT population at each site and within each country and region will be presented.

The proportion of subjects in the AT population who withdrew from the study, and the reported reasons for withdrawal, will be presented. A Kaplan-Meier plot presenting the percentage of subjects withdrawing from the study over time will be produced for the AT Population.

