4. SUBJECT SELECTION AND WITHDRAWAL CRITERIA

4.1. Number of Subjects

Approximately 375 subjects are estimated to be eligible to take part in this study. As the study is open-label, no randomization will occur. Attrition/withdrawal is expected to be less than 10% of enrolled subjects.

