4.4.3. Withdrawal By Investigator

4.4.3.1. General Withdrawal Requirements

Subjects may be withdrawn from study treatment at anytime by the investigator if it is deemed detrimental for them to continue in the study. Reasons for withdrawal can include: an adverse event, lost to follow-up, protocol violation, lack of efficacy, sponsor terminated study, non-compliance, abnormal laboratory results (Section 6.3.3), or for any other reason.

Subjects may also be withdrawn from this study if mepolizumab becomes commercially available in the respective country, if marketing of mepolizumab is no longer being sought in the respective country, or upon decision of the sponsor to discontinue further development of mepolizumab. Every effort should be made to have the subject complete the Exit/Early Withdrawal Visit.

A subject must be permanently discontinued from IP if any of the following stopping criteria are met:

- **Liver Chemistry:** Meets any of the protocol-defined liver chemistry stopping criteria (Section 11.4).

- **Pregnancy:** Positive pregnancy test

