## 11.6. Appendix 6: Reporting Standards for Missing Data

### 11.6.1. Premature Withdrawals

Element	Reporting Detail
General	
 
Subjects will receive mepolizumab 100 mg SC every for weeks, but it is expected that subjects would withdraw before the Exist Visit due to NUCALA becoming commercially available before the end of the study. Thus, this study will not have any completers and all subjects will eventually withdraw (See Section 2.3).
 
Withdrawn subjects will not replaced in the study.
 
All available data from subjects who were withdrawn from the study will be listed and all available planned data up to and including the date of early withdrawal will be included in summary tables and figures, unless otherwise specified.
 

	
 
Early withdrawal visits will be slotted as per Appendix 2: Assessment Windows.
 

Screen Failures	
 
For the purposes of this study screen failures will be defined as follows:
 
Subjects will be assigned a study number at the time of signing the informed consent (Baseline Visit).
 
Those subjects that complete at least one Visit 1 (Baseline Visit) procedure but do not subsequently receive study treatment will be designated as screen failures.
 

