### 11.10.5. Study Population Figures

Study I	Study Population: Figures							
No.	Population	IDSL / TST ID / Example Shell	Title	Programming Notes	Deliverable			
Subjec	t Disposition							
1.1	AT	SHELL	Time to End of Study	See Study Population Figure 1.1 (MEA117113 'final' reporting effort), but exclude 'Placebo' and Mepo 300mg SC	SAC			

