2.17.	AT	SHELL	Summary of Post-Treatment Adverse Events by Highest Anti Drug Antibody Result At Any Time Post Baseline		SAC			

Safety: Tables							
No.	Population	IDSL / Example Shell	Title	Programming Notes	Deliverable		
2.18.	AT	AE15	Summary of Common (>=3%) Non-serious Adverse Events by System Organ Class and Preferred Term (Number of Subjects and Occurrences)	FDAAA, EudraCT ≥3% (prior to rounding to nearest percent)	SAC		
Serious	and Other Sig	nificant Adverse	Events				
2.19.	AT	AE1	Summary of Pre-Treatment Serious Adverse Events by System Organ Class and Preferred Term		SAC		
2.20.	AT	AE1	Summary of On-Treatment Serious Adverse Events by System Organ Class and Preferred Term		SAC		
2.21.	AT	AE1	Summary of Post-Treatment Serious Adverse Events by System Organ Class and Preferred Term		SAC		
2.22.	AT	SHELL	Summary of Exposure Adjusted On-Treatment Serious Adverse Events by System Organ Class and Preferred Term		SAC		
2.23.	AT	SHELL	Summary of On-Treatment Serious Adverse Events by Age Group (12-17, 18-64, >=65 years)		SAC		
2.24.	AT	AE1	Summary of Fatal Serious Adverse Events		SAC		
2.25.	AT	SHELL	Summary of Fatal Serious Adverse Events by Age Group (12- 17, 18-64, >=65 years)		SAC		
2.26.	AT	AE1	Summary of Non-Fatal Serious On-Treatment Adverse Events by System Organ Class and Preferred Term		SAC		
2.27.	AT	AE1	Summary of Non-Fatal Serious Post-Treatment Adverse Events by System Organ Class and Preferred Term		SAC		
2.28.	AT	SHELL	Summary of Exposure Adjusted On-Treatment Non-Fatal Serious Adverse Events by System Organ Class and Preferred Term		SAC		

Safety:	Safety: Tables							
No.	Population	IDSL / Example Shell	Title	Programming Notes	Deliverable			
2.29.	AT	AE1	Summary of Drug-Related Fatal Serious Adverse Events by System Organ Class and Preferred Term		SAC			
2.30.	AT	AE5	Summary of Drug-Related Serious Adverse Events by System Organ Class and Preferred Term and Maximum Intensity	Add a Total column across all severities	SAC			
2.31.	AT	AE3	Summary of Adverse Events Leading to Permanent Discontinuation of Study Treatment or Withdrawal from Study by System Organ Class and Preferred Term /by Overall Frequency	IDSL	SAC			
2.32.	AT	SHELL	Summary of Exposure Adjusted On-Treatment Adverse Events Leading to Permanent Discontinuation of Study Treatment or Withdrawal from Study by System Organ Class and Preferred Term		SAC			

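### Does the withdrawal curve need a censoring rule for commercial launch, and does lack-of-efficacy withdrawal need an exposure-adjusted display?

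*SAP*

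**What the plan says.** SAP 6.2 promises the proportion of As Treated subjects who withdrew, the reported reasons, and a plot: "A Kaplan-Meier plot presenting the percentage of subjects withdrawing from the study over time will be produced for the AT Population". The display list (SAP 11.10.5) titles it "Time to End of Study" and points to a figure from another study for its layout. The shells are not reproduced in the SAP.

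SAP 11.6.1 expects subjects to leave when the product is launched, so that "this study will not have any completers and all subjects will eventually withdraw". The first condition for the final analysis in SAP 3.2 is: "All subjects have been withdrawn from the study as defined in the protocol". Protocol 4.4.3.1 gives the launch ground: "Subjects may also be withdrawn from this study if mepolizumab becomes commercially available in the respective country". Under Protocol 3.1, closure proceeds country by country.

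The secondary endpoints in SAP 2.2 include "Number of withdrawals due to lack of efficacy" and, in the same form, the number due to adverse events. Reasons appear in Table 1.6 and Listing 3. For adverse events the SAP also lists Table 2.32: "Summary of Exposure Adjusted On-Treatment Adverse Events Leading to Permanent Discontinuation of Study Treatment or Withdrawal from Study". Protocol 4.1 adds a planning remark: "Attrition/withdrawal is expected to be less than 10% of enrolled subjects".

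**The concern.** A Kaplan-Meier plot normally needs a stated event and a stated censoring rule, and SAP 6.2 gives neither. Because everyone is expected to withdraw, an all-cause curve must finish at 100%, and once countries start to close it mainly traces launch dates. A reader who took it for attrition and set it beside the protocol's figure of under 10% would be misled.

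The second worry is unequal opportunity. A subject in a country that closes early has less time in which to withdraw for lack of efficacy, so the crude count depends on launch timing as well as on treatment failure. The SAP allows for exposure elsewhere: exacerbations use a log-time offset (8.1.5.1) and adverse events have exposure-adjusted rates (7.2). Leaving this one secondary endpoint as a raw count looks inconsistent, and a description of long-term experience could be harder to interpret as a result.

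**Working it through.** The plan states no figure to reproduce here, so the check sets the sections side by side and then sizes the effect of closure timing.

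**1. Is a censoring rule needed for Figure 1.1?**
- SAP 6.2 plots withdrawal from the study without restriction by reason.
- SAP 11.10.5 titles the figure as time to end of study.
- SAP 11.6.1 expects no completers.
- SAP 3.2 delays the final analysis until every subject has been withdrawn.
- Protocol 4.4.2 makes loss to follow-up a withdrawal reason too.

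Together these make any withdrawal the event, with every end date known at database freeze. With no censoring, the Kaplan-Meier estimate is simply the observed proportion withdrawn by each week. A subject who did reach Week 172 would affect only the last step of the curve.

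**2. What is delivered for lack of efficacy?**
- The endpoint is a number. Table 1.6 gives withdrawals by reason and Listing 3 gives them by subject.
- Time on treatment is summarised in Table 2.1, and exposure data are listed in Listing 9. SAP 11.5.4 defines days of exposure as last dose minus first dose plus 29.
- A crude rate therefore follows: 1000 × (subjects withdrawn for lack of efficacy) ÷ (total exposure days ÷ 365.25).

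**3. How far could closure timing move a crude percentage?**

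The documents give about 375 subjects and a maximum of 172 weeks. The following are assumptions: 10% non-closure withdrawal by Week 172, a constant hazard, and closure dates uniform between weeks a and b.

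- Hazard: h = −ln(0.9)/172 = 0.000613 per week.
- Crude proportion: 1 − [exp(−ha) − exp(−hb)] / [h(b − a)].
- Mean follow-up: crude proportion ÷ h.

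| Closure window (weeks) | Crude | Of 375 | Mean follow-up (years) | Per 1000 subject-years |
|---|---|---|---|---|
| 48–120 | 5.0% | 18.8 | 1.57 | 32.0 |
| 60–172 | 6.8% | 25.7 | 2.14 | 32.0 |
| 100–172 | 8.0% | 29.9 | 2.50 | 32.0 |

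If the 10% is placed at Week 120 instead, the first and last rows become 7.1% and 11.2%, at 46 per 1000 subject-years.

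For the 48–120 window the all-cause curve is 1 − exp(−ht)(120 − t)/72, and the curve censored at closure is 1 − exp(−ht):

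| Week | All-cause | Censored at closure |
|---|---|---|
| 48 | 2.9% | 2.9% |
| 84 | 52.5% | 5.0% |
| 120 | 100% | 7.1% |

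The two curves answer different questions. The constant rate is built in: mean follow-up is crude ÷ h, so crude divided by follow-up must return h. The tables show a direction under invented closure dates, and they cover all non-closure withdrawal. If lack of efficacy were one fifth of it (a further assumption), 19 to 30 subjects would become about 4 to 6.

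**4. Is Table 2.32 a true parallel?**

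The SAP 11.5.4 formula puts the number of adverse events in the numerator, and Table 2.32 is broken down by system organ class and preferred term. One subject can contribute several events. It is not a rate of withdrawn subjects, so the adverse-event withdrawal endpoint also has no person-level exposure-adjusted display.

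**The case for a change.** The strongest case for a change is that the SAP accepts the need to allow for exposure elsewhere, that closure by country makes follow-up unequal by design, and that the secondary objective is to describe long-term experience, which a count that moves with launch dates describes imperfectly. The primary reason for withdrawal is already recorded (Protocol 4.4.5), so a rate would cost little.

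Part of this stands. No rate or cumulative-incidence display for lack-of-efficacy withdrawal is listed, and the crude percentage does depend on closure timing. A report author could usefully add one line giving subjects withdrawn for lack of efficacy, and subjects withdrawn for adverse events, per 1000 subject-years. That is optional, and it should not be set beside the event counts of Table 2.32.

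The rest is weaker. Neither document plans to compare Figure 1.1 with the under-10% remark, which has no time horizon and supports no calculation. A curve censored at closure would need launch-driven exits to be separable from other reasons. The reasons named in Protocol 4.4.3.1 include termination by the sponsor, but commercial availability is given only as a separate ground, so the documents do not show that the recorded reason isolates it. Such a curve would also assume that closure is unrelated to a subject's response.

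**Conclusion.** No change follows. The absent event definition is a gap in wording that the SAP's own statements close: Figure 1.1 is an all-cause curve to end of study, already titled as such, and it should not be read as attrition. The lack-of-efficacy endpoint is reported as defined, as a count with reasons, and the planned exposure outputs allow a crude rate. The possible distortion, 5.0% to 8.0% crude withdrawal at one fixed rate, rests on assumed closure dates and an assumed 10%, and it concerns all non-closure withdrawal; the size for lack of efficacy alone cannot be derived from the documents. With a single arm, no hypothesis and no treatment comparison (Protocol 8.1 and 8.3.3), the plan as written gives sound counts by reason, and further displays would change no result or conclusion. This conclusion relies on the SAP's expectation that all subjects will have withdrawn before the final analysis.
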